#### Randomization procedures

A randomization manager from FHI 360, who is not otherwise involved in the study, will prepare a computerized randomization list using permuted blocks before the start of the study. These envelopes

---

a A total of 342 DMPA acceptors will be distributed among the 5 health facilities in urban Karachi district. On average, about 68 acceptors will be recruited per facility of which half will be assigned to LHWs.

[figure not shown]
will be given to the local PI at AKU who will distribute the envelopes to RAs assigned to study health facilities. These RAs will open the randomization envelopes and inform LHWs or LHV when they have been selected to provide DMPA services (screening, counseling) and which form of DMPA (IM or SP) they will provide after the independent third party verifies the client's eligibility for DMPA use.

Women will be randomized in a 1:1 ratio to proceed with DMPA screening by an LHV or LHW. After the independent staff member confirms the client's eligibility to use DMPA, an identical randomization procedure will be performed to randomize women to receive either DMPA IM or SP. The master randomization list will be maintained at FHI 360 and will not be available to study staff.

Randomization groups will be concealed in sequentially numbered, sealed opaque envelopes (SNOSE). We will instruct study staff never to open an envelope until the participant has given consent to participate in the study, is found to be eligible for the study, and is present for DMPA screening and the subsequent administration of the injectable. These envelopes will be provided to AKU in advance of trial implementation. The opened randomization envelopes will be retained as source documents and will be kept under secure and restricted access to protect the confidentiality of the participants.

This is an open-label study – neither study staff nor participants will be blinded to study treatment arms after the point of randomization. Nonetheless, strict policies will be in place to preserve randomization integrity. Randomization documentation will be stored in a secure location. Data recording, assessment of the primary and secondary study outcomes, and other assessments, such as DMPA eligibility assessment by independent facility staff, will be blinded to treatment arm where possible. The FHI 360 lead statistician and data analysts will perform a blinded review of the data to make final statistical decisions that could affect the comparison of the primary and secondary outcomes before fully unblinding the data for final analyses. Details of the analysis processes will be described in the detailed analysis plan.

Screening, counseling and DMPA administration will all be performed by the same LHW or LHV randomized to provide services to that client. The receipt of DMPA IM or SP is being randomized to avoid an imbalance of DMPA type that could occur if clients are given the choice between the two delivery systems. Similarly, provider bias/preference for one form or the other of DMPA could result in the same. The following graphic describes the procedures, including randomization, to be adopted in this trial.

## Data collection procedures

### *Observation of screening and counseling*

After the DMPA client has provided informed consent and been randomized to see an LHW or an LHV, the RA posted at the study site will observe the screening and counseling interaction between the LHW/LHV and client. The RA will request that the interaction be conducted in accordance with the health facility's privacy policy and with the normal procedure for client-provider interaction. As such, we are currently unable to specify a range of time in which these observations will be performed.

The RA will first record observations using the first part of the checklist devoted to screening for client eligibility. If the LHW/LHV deems the client eligible for DMPA, then the RA will record whether or not the LHW/LHV proceeded to deliver key counseling elements of DMPA use to the client. All data will be recorded via pen and paper to be later entered into an electronic database.

After the client has been counseled, the clinic staff assigned at that study site to provide support to the trial will verify that the client is indeed eligible to receive DMPA. The staff member will serve as the independent gold standard for LHW and LHV performance. If s/he confirms that the client is eligible for DMPA use, the client will then receive DMPA subcutaneously or via an intramuscular injection from the same LHW or LHV who earlier screened and counseled her. If the staff member determines that the woman is not eligible for DMPA use, she will be offered another method and released from participation in the trial. The LHV/LHW who incorrectly deemed the client eligible for DMPA will not be penalized and the event will be treated and utilized as a learning experience.

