### III. Methodology

#### *Overview*

This will be a randomized controlled trial conducted in Sindh Province, Pakistan, using quantitative methods. Third-party, independent data collectors will be trained to perform onsite observations of screening and counseling of first-time DMPA clients performed by LHWs and LHV in health facilities. Another health facility provider--blinded to the LHW or LHV who provided the initial screening--will verify client eligibility to use DMPA through their own client interview. If the independent screener deems the client eligible to receive DMPA, then the same provider who earlier screened and counseled her on the method will administer the injectable to her. Clients will also be randomized to receive DMPA IM or SP to prevent selection biases between these groups. However, comparisons between these injection techniques will only be considered exploratory, focusing instead on acceptability of and satisfaction with the method as reported by clients.

Survey interviews with participating LHWs and LHV will be conducted four to six months after trial initiation to obtain their feedback on providing DMPA IM and SP and attitudes towards LHW-initiation of injectables.

The study is limited to participating LHWs, LHV and to their clients who voluntarily and independently accept DMPA as their contraceptive method before study recruitment is initiated.

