Data Cleaning

The Department of Community Health Sciences, Aga Khan University (AKU), Pakistan, the local research agency, will create database shells. FHI 360 will review database structures and documentation prior to data entry. AKU will use a system of double data entry and frequency checks to minimize data entry errors for all interview instruments. A study coordinator at AKU will oversee day-to-day management of the trial. Clean databases will be sent to FHI 360’s data manager for verification according to the timeline for those deliverables. FHI 360’s data manager will provide access to the blinded data to the analysis team for blind review of the data and unblinded data for final analyses when the data analysis team is ready (see details below).

No imputation of missing data will be performed. However, to decrease the number of cases when composite measures for observations of injection technique may be missing, where less than 15% of the items are missing among variables needed for deriving composite variables, we may decide to impute the mean of the non-missing items. Missing data will be noted in Table or Figure footnotes. Proportions and mean/median values will be calculated with missing data excluded from the denominator.

During all phases of data collection, entry, cleaning and verification, access to hard copy and electronic data will only be granted to research staff at AKU and FHI 360. Hard copies of interviews, observation checklists and other materials containing study data will be stored in a locked file cabinet at AKU. Informed consent forms will be stored in a separate locked drawer or cabinet. Electronic data will be

stored in password-protected files. Only staff working on the study will have access to the cabinets and electronic files. Upon completion of the trial, all stored materials will be destroyed at AKU. However, no records will be destroyed without permission from the FHI 360 project leader.

C. Definition of Variables

Key primary outcomes will be calculated as follows.

Screening for DMPA use

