There are 15 screening questions on the job aid that providers use to determine if a client is or is not a good candidate for DMPA or needs further evaluation before initiating DMPA. The provider makes a global decision of eligibility or ineligibility based on the job aid items and whether or not she would subsequently initiate the client on DMPA. The observer notes the provider's decision whether to start the client on DMPA. This global decision (and not agreement on every screening item), is compared with the gold-standard nurse's assessment of client eligibility to generate the outcome variable for appropriate screening. Thus, the gold standard nurse's overall assessment of eligibility is made after the provider's assessment, and s/he is the final arbiter of eligibility. Thus, if the gold standard nurse determines that the client is eligible to use DMPA, the latter will receive the injectable regardless of the provider's assessment. To avoid bias, the gold standard nurse is blinded to the type of provider who assessed the client beforehand. Whether or not they are deemed eligible to use DMPA as their chosen method, all clients will receive counseling appropriate to their circumstance.

Counseling for DMPA use

Appropriate counseling is a composite binary variable that will be calculated from observations of the discussion between the provider and client. If the provider spoke to the client about side effects, warning or danger signs, advantages, and disadvantages of DMPA, then the conditions are met for appropriate counseling (all conditions must be met for considering the counseling appropriate). If any is missing, the counseling is deemed inappropriate. These variables will also be presented separately in the descriptive analyses by type of provider (and urban/rural setting if the data are not pooled).

Appropriate injection technique

Appropriate injection technique is assessed using checklists for DMPA-IM and DMPA-SC previously developed and validated for this purpose. To meet the criteria for appropriate administration of the injection, the provider must complete 80% of the items on the checklist (i.e., at least 18 out of 22 for SP and at least 14 out of 17 for IM).

D. Blind Data Review

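### The Protocol's field procedure describes independent verification only for women the provider has cleared and counselled, while the SAP's primary outcome needs a nurse decision on every randomised woman, so wrong refusals could go uncounted

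*Protocol*

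**What the plan says.** The Protocol section on observation of screening and counseling sets out one path. The provider screens. Then: "If the LHW/LHV deems the client eligible for DMPA, then the RA will record whether or not the LHW/LHV proceeded to deliver key counseling" content. Next: "After the client has been counseled, the clinic staff assigned at that study site to provide support to the trial will verify" that the woman qualifies. If the check confirms this, the same provider injects; if not, the woman is offered another method and leaves the trial. The only disagreement named is a wrong clearance: "The LHV/LHW who incorrectly deemed the client eligible for DMPA will not be penalized". Nothing says where a woman goes if the provider turns her down.

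The Protocol Overview is less restrictive. It says that another facility provider "will verify client eligibility to use DMPA through their own client interview", with no condition on what the first provider decided. A graphic of the procedures is announced at the end of the Randomization procedures section, but it is not in the text available for review.

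The SAP (V.C, Screening for DMPA use) takes the provider's overall decision, eligible or ineligible, which "is compared with the gold-standard nurse's assessment of client eligibility to generate the outcome variable for appropriate screening". It makes the nurse the final arbiter: "if the gold standard nurse determines that the client is eligible to use DMPA, the latter will receive the injectable regardless" of what the provider decided. SAP VIII repeats that appropriate screening means agreement between the two assessments.

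On missing data, SAP V.B states: "Proportions and mean/median values will be calculated with missing data excluded from the denominator". The only imputation it allows is for composite measures of injection technique. SAP V.D plans an intention-to-treat primary analysis of all randomised women, subject to changes made at blind review.

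**The concern.** A provider can make two kinds of screening error: clearing a woman who should not start, and refusing one who could. The SAP outcome counts both. The Protocol's field procedure produces a reference decision only for women on the cleared path, so a site that follows it as written can detect only the first kind.

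Refusal is an expected result. The observation checklists in both documents have branches for telling a woman she is not a good candidate, referring her, or asking her to return later. None of these branches leads to the independent assessor.

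A refused woman without a nurse decision has no primary outcome, and the SAP's missing-data rule removes her. The quantity analysed then becomes the proportion correct among cleared women, which is not the proportion appropriately screened among all randomised women. A cadre that over-refuses would look as accurate as one that does not. The trial is meant to inform national policy and WHO guidance on whether LHWs can screen for initiation as well as LHVs. The analysis cannot recover a nurse decision that was never collected.

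**Working it through.** **The plan's own figure.** Inputs from the Protocol, Sample size: 95% success in both arms, margin 7.5 points, 90% power, 5% level, 342 women (171 per arm). At one-sided 5% the simple formula gives n = 2(0.95)(0.05)(1.645 + 1.282)²/0.075² = 144.6 per arm. With a continuity correction, n = (144.6/4)[1 + √(1 + 4/(144.6 × 0.075))]² = 170.3, so 171 per arm and 342 in total. The Farrington-Manning variance gives 170.4, also 342. The stated size is therefore reproduced at one-sided 5%. SAP V.E sets two-sided 0.05, so the main case below is also given at one-sided 2.5%.

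**Who gets a nurse decision.**

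| Provider's decision | Protocol, observation section | SAP V.C and VIII |
|---|---|---|
| Eligible | Verified after counselling | Compared with nurse |
| Ineligible | No step described | Compared with nurse; nurse's finding of eligibility prevails |

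**Effect if refused women are not verified.** Let w be the share wrongly cleared and r the share wrongly refused, with no correct refusals.

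- Agreement with all women verified: 1 − w − r
- Agreement among cleared women: (1 − w − r)/(1 − r) = 1 − w/(1 − r)

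The documents give neither w nor r. Assume w = 3% in both arms and r = 2% for LHVs.

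- LHV: all verified 1 − 0.03 − 0.02 = 95%. Cleared only 1 − 0.03/0.98 = 96.9%, n = 171 × 0.98 ≈ 168.
- LHW with r = 10%: all verified 1 − 0.03 − 0.10 = 87%. Cleared only 1 − 0.03/0.90 = 96.7%, n = 171 × 0.90 ≈ 154.

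A true deficit of 8 points is measured as about 0.3 points. The probability of declaring non-inferiority, by exact binomial enumeration with the Farrington-Manning test, margin 0.075, one-sided 5%, no clustering, is:

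| LHW wrong refusals | True LHW vs LHV | Inside margin? | All verified | Cleared only |
|---|---|---|---|---|
| 10% | 87% vs 95% | No | 3.5% | 94.8% |
| 7.5% | 89.5% vs 95% | Yes | 16.6% | 95.9% |
| 5% | 92% vs 95% | Yes | 49.3% | 96.3% |
| 2% | 95% vs 95% | Yes | 92% | 97% |

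At one-sided 2.5% the first row becomes 1.6% and 87.9%.

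**Range under other assumptions.** Put LHWs exactly at the margin (95% vs 87.5%), with 171 per arm, an unpooled Wald test at one-sided 5%, LHV wrong refusals from 0 to 5%, and correct refusals of 0 or 5%. With all women verified, false non-inferiority is 5%. With cleared women only, it depends on how much of the LHW excess error is wrong refusal: about 2 to 5% if none, 29 to 69% if half, and 86 to 100% if all.

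**The case against.** The strongest reply is that the Protocol nowhere limits verification to cleared women. The conditional in its observation section governs what the research assistant records about counselling. The verification sentence depends only on counselling having taken place, and SAP V.C says all clients are counselled, eligible or not. The Protocol Overview is unconditional, SAP V.B places the nurse's assessment directly after the provider's screening, and the graphic that is not shown may contain a refusal path. Read together, the documents can be taken to send every woman to the nurse.

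Much of this stands, and it limits the point in four ways.

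- A reader might infer that the Protocol bars verification of refused women. It does not. The restriction is inferred from the order of steps, from verification being framed as confirmation, and from the single error named.
- A reader might infer that the documents contradict each other on a refused woman whom the nurse finds eligible. The Protocol is silent there and the SAP is explicit, so this is a gap.
- A reader might infer that the bias always favours LHWs. It does so only if they wrongly refuse more. With the rates reversed (LHV 10%, LHW 2%), a true 8-point LHW advantage is measured as about 0.3 points, and declaration falls slightly, from 100% to 98%.
- A reader might take every row of the table as a false conclusion. Wrong refusals of 5% and 7.5% leave LHWs 3 and 5.5 points worse, inside the margin, so declaring non-inferiority there is correct. Only the 10% row breaches it.

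The reply does not remove the gap. Site staff work from the field procedure, and that text leaves out half of what the primary outcome requires.

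**Conclusion.** The point holds as a gap between the Protocol's field procedure and the SAP's primary outcome. If sites follow the procedure as written, refused women have no outcome, the missing-data rule drops them in conflict with the intention-to-treat statement, and wrong refusals are not counted. If sites follow the SAP, they are counted.

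The size of any bias cannot be derived from the documents, because they give no refusal rates and no split of errors. It is negligible if wrong refusals are rare or similar by cadre. It could reverse the conclusion if LHWs wrongly refuse many more: in the illustration, non-inferiority is declared in 95% of trials instead of 3.5%, with LHWs truly 8 points worse. That case assumes a fivefold difference in wrong refusals, equal wrong clearances, no correct refusals and no clustering.

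**What to change.** 1. In the Protocol's observation section, state that every randomised woman, whatever the provider decided, has the blinded independent assessment, recorded for the primary outcome. Align the Randomization procedures section and, if needed, the graphic. The SAP already assumes this.
2. In the SAP, report by arm and by provider decision the number of randomised women without a nurse decision.
3. Add a sensitivity analysis that keeps refused women who have no nurse decision and varies their outcome, by arm, from all correct to all incorrect. Scoring them all as inappropriately screened is not suitable, since it would count correct refusals as provider errors. In the 10% illustration the bounds are 87% to 97% for LHWs and 95% to 97% for LHVs. The difference then runs from −10 points (87 − 97) to +2 (97 − 95), which contains the true −8.
4. Reconcile the Protocol's observation section with SAP V.C on counselling and care of a woman the provider refused. Which rule applies is for the clinical team.

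The cost is wording in both documents, plus one short interview per refused woman by staff already assigned at the site. Sample size is unchanged. The Protocol change has to precede data collection.

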### *Client exit interview*

After receipt of her first dose of DMPA, the RA will conduct a brief interview with the client before she leaves the health facility, at a designated area in or within 500 feet of the site that provides audio privacy. The interview is expected to take between 10 and 15 minutes.

### *LHW/LHV interview*

About four to six months after trial initiation, some participating LHWs and all LHVs will be asked for their permission (via informed consent) to be interviewed by an RA. By that time, they would have all provided initial and follow-up injections to their DMPA clients and should be able to describe their experiences. LHVs and LHWs will be interviewed at their assigned study sites.

As part of the interview process for LHWs only, the RA will be asked in advance of the meeting to bring their DMPA client materials with them. The RA will examine DMPA client records to verify that injection and re-injection dates are being recorded appropriately. Thus, as one of the objectives of the study, we will ascertain whether or not LHWs diligently record the dates of service for DMPA clients, how many are first-time or repeat DMPA clients, and if re-injection dates were scheduled for all of them. For LHWs who do not bring their logbook with them to the interview, a second and final session will be scheduled to capture that information. No additional attempts will be made to gather that information from the LHW and the data will be considered missing for that LHW.

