FHI 360 and Jhpiego in collaboration with USAID, Aga Khan University (AKU) and the Government of Sindh province propose a randomized controlled trial (RCT) to provide evidence needed not only to change current policies in Pakistan forbidding initiation of DMPA by LHWs, but also for WHO to consider

modifying the recommendation for targeted M&E for lay health worker provision of intramuscular injectable contraceptives. The trial will be conducted in Pakistan with Lady Health Workers (LHWs)—the main lay health worker cadre. Given the very large number of LHWs—perhaps as much as 150,000^13—this trial could just as importantly facilitate access to injectable contraception for thousands of Pakistani women, potentially increasing the country's modern contraceptive prevalence rate (mCPR).

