## **II. Objectives and Outcomes**

The overall goal of the trial is to provide high-level evidence that lay or community health workers can safely and effectively screen and initiate women who choose to use injectable contraceptives. The primary objective is:

To assess whether the community health worker cadre, Lady Health Workers (LHWs) in Pakistan can screen and initiate women on intramuscular and subcutaneous Depo Provera injections as safely and effectively as their clinically-trained counterparts, Lady Health Visitors (LHVs).

Although LHWs are already allowed to provide follow-up doses in the community, this RCT will focus on the comparison of safety and effectiveness of screening, counseling and first-time administration of DMPA IM and SP. Rather than focusing on determining whether services are better provided by one of the two health worker cadres, we want to determine if LHWs can perform just as well as the more experienced LHVs. Therefore, the trial will be powered specifically to detect non-inferiority (i.e., no difference) within a tolerance margin in the performance of LHWs compared to LHVs with regard to screening--the procedure that determines a woman's eligibility to receive DMPA. We consider the assessment of the screening for DMPA use as the primary outcome of interest for addressing the primary objective. However, in addition to screening, metrics for counseling and administration of DMPA will constitute the endpoints for the primary objective described below:

- Proportion of Lady Health Workers and Lady Health Visitors that appropriately screen women for DMPA use;
- Proportion of Lady Health Worker and Lady Health Visitor clients that report discussion with their respective providers on side effects, danger signs, advantages and disadvantages of DMPA use;
- Proportion of Lady Health Workers and Lady Health Visitors that demonstrate appropriate injection technique
- Proportion of Lady Health Workers and Lady Health Visitors that report needle stick injuries;
- Proportion of Lady Health Workers that properly maintains a client (re)injection log.

Details on analysis of these endpoints will be provided in a separate data analysis plan.

The secondary objective is:

To assess whether DMPA clients of Lady Health Workers and Lady Health Visitors are equally satisfied with their respective providers and the family planning services they provide.

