### *Lady Health Workers*

Selections will be based on LHW affiliation to the 10 health facilities in Sindh chosen to take part in the trial. Jhpiego will make the final selection of LHWs to be trained and to participate in the trial, which will be based on the following criteria:

- Already trained to provide follow-up DMPA IM injections in their community;
- Currently providing services in their community
- Willingness and ability to participate in the trial

Jhpiego will develop relevant materials and tools to carry out the training of LHWs to screen and counsel first-time DMPA users—both IM and SP acceptors. LHWs will also be trained, or if already experienced in this area, given a refresher on maintaining DMPA client records and re-injection logs—adapting existing Pakistani forms if necessary. Jhpiego’s training materials will be reviewed with the study team to ensure that the content is aligned with study objectives and procedures.

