### ***Study procedures***

#### **Data collection instruments**

FHI 360 Headquarters (HQ) staff will develop two survey questionnaires and three observation checklists for screening and counseling first-time DMPA acceptors. One questionnaire—an exit interview-- will be administered to DMPA clients, and the other, to LHWs and LHV four to six months after initiation of the trial. Interviews with LHWs will be conducted during one of their routine visits to the health facility for resupply and supervision. LHWs will also be asked to present their family planning records at that time to determine if they properly maintain their injection and re-injection log books. Questions specific to LHWs and to LHV will be arranged in separate sections of the instrument with appropriate skip patterns.

Three observation checklists will be developed for screening and counseling DMPA users. Independent observers will document screening and counseling procedures employed by LHWs and LHV on one checklist, while the other two checklists will document injection technique separately for DMPA IM and SP.

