Use of client (re)injection log*	Descriptive	urban/rural	LHW/LHV questionnaire, qLHW6
Objective 2 Outcomes			
Client satisfaction with DMPA*	Descriptive	Cadre, DMPA type	Client exit interview, q313
Client satisfaction with service delivery*	Descriptive	Cadre, DMPA type	Client exit interview, q318
Client comfort asking provider questions*	Descriptive	Cadre, DMPA type	Client exit interview, q303
Friendly and respectful behavior by provider*	Descriptive	Cadre, DMPA type	Client exit interview, q301

* If the data are pooled, there will be no urban/rural stratification

Objective 1 Table Shells: Screening and counseling for DMPA

Table 1: Odds of appropriate screening and counseling for DMPA initiation by Lady Health Workers compared with Lady Health Visitors in Pakistan

OR	90%CI	p-value
Appropriate screening		
Appropriate counseling		

Appropriate screening defined as agreement between the provider and independent assessment by a gold standard nurse
Appropriate counseling defined as having discussed side effects, warning/danger signs, advantages, and disadvantages of DMPA

95% CI and p-value reported for test of non-inferiority

Table 2: Exploratory analysis of factors affecting appropriate screening for DMPA initiation by Lady Health Workers compared with Lady Health Visitors in Pakistan

	N (%)	OR (or β)	95%CI	p-value
Age				
Age cat 1				
Age cat 2				
Etc.				
Marital status				
Marital status 1				
Marital status 2				
Etc.				
Education level				
Education level 1				
Education level 2				
Etc.				
Years of service				
Categorical or continuous TBD				
Years of DMPA experience				
Categorical or continuous TBD				
Avg. DMPA injections/month				
Categorical or continuous TBD				

Appropriate screening defined as agreement between the provider and independent assessment by a gold standard nurse

Table 3: Exploratory analysis of factors affecting appropriate counseling for DMPA initiation by Lady Health Workers compared with Lady Health Visitors in Pakistan

	N (%)	OR (or β)	95%CI	p-value
Age				
Age cat 1				
Age cat 2				
Etc.				
Marital status				
Marital status 1				
Marital status 2				
Etc.				
Education level				
Education level 1				
Education level 2				
Etc.				
Years of service				
Categorical or continuous TBD				
Years of DMPA experience				
Categorical or continuous TBD				
Avg. DMPA injections/month				
Categorical or continuous TBD				

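### The log outcome is assessed only from the LHW's own records, so a trial client missing from all of them would go unnoticed, although the trial can count first doses per LHW independently

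*Protocol*

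**What the plan says.** Protocol II (Objectives and Outcomes) lists among the endpoints of the primary objective: "Proportion of Lady Health Workers that properly maintains a client (re)injection log". SAP I repeats it as a primary outcome. It has no LHV counterpart.

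The assessment takes place at the provider interview, four to six months after the trial starts. The LHW is to bring her DMPA materials, and a second session is arranged if the logbook is left behind. The protocol (LHW/LHV interview) then says: "The RA will examine DMPA client records to verify that injection and re-injection dates are being recorded appropriately". It adds: "we will ascertain whether or not LHWs diligently record the dates of service for DMPA clients". The RA is also to establish "how many are first-time or repeat DMPA clients" and whether re-injection dates were scheduled for all of them.

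SAP VIII, Table 2, gives the source as "LHW/LHV questionnaire, qLHW6" and the analysis as descriptive. SAP V.C gives rules for screening, counseling and injection technique. It gives none for proper maintenance of the log.

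**The concern.** Reading a log can show whether the clients in it have complete dates. It cannot show whether a client was never entered. In the instruction to check that re-injection dates were scheduled for all clients, the word all can reach only the women the LHW wrote down somewhere. A client absent from all her papers leaves no trace at this step.

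The outcome is one of five offered in support of the claim that LHWs can initiate DMPA as safely and effectively as LHVs. If omissions occur and are not seen, the reported proportion could be too high. The trial could look for them, because its own staff are present when the first dose is given.

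**Working it through.** **1. What is compared with what.**
- Source for the outcome: the LHW's own client records and logbook (protocol, Data collection instruments and LHW/LHV interview), captured through one questionnaire item (SAP Table 2).
- Outside comparator named: none in either document.
- Independent information the trial generates: the RA observes the first injection (protocol, Pilot testing and recruitment procedures), the client is interviewed before leaving (Client exit interview), and opened envelopes are kept as source documents (Randomization procedures).
- Count per LHW: the protocol interviews only LHWs with at least nine new clients, or four at rural sites, and that requires a count. SAP V.B instead has all participating LHWs asked for an interview. The count is still available, because the mixed model in SAP VIII has a random effect for provider and so needs each client's provider.

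**2. The plan's own figure.** The protocol footnote spreads 342 clients over 5 urban facilities, half to LHWs. 342/5 = 68.4 and 68.4/2 = 34.2, which matches the stated figure of about 34 per facility.

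**3. Trial clients per LHW.** There are three LHWs per facility (Sample size; SAP Table 1 has 30 LHWs for 10 facilities).
- Urban: 34.2/3 = 11.4.
- Rural: about 100 clients over 5 facilities, half to LHWs: 100/5/2 = 10, and 10/3 = 3.3.

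These are clients assigned. Women whom the independent screener finds ineligible receive no dose, so the number of checkable doses is somewhat smaller.

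**4. Illustration.** The documents give no omission rate. Let q be an assumed chance that a trial client is missing from all the LHW's papers, independent between clients, and m the number of first doses. The chance of at least one omission is 1 - (1 - q)^m.

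| m | q = 5% | q = 10% | q = 20% |
|---|---|---|---|
| 11 (urban average) | 43% | 69% | 91% |
| 9 (urban interview threshold) | 37% | 61% | 87% |
| 4 (rural interview threshold) | 19% | 34% | 59% |

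For example, 1 - 0.9^11 = 0.69. If every trial client is expected in the log, these are also the chances that a full comparison with trial records would reveal an omission. Reading the LHW's papers alone reveals none of these omissions at any q.

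**5. Sensitivity to clustering.** Omissions may concentrate in a few LHWs. Under a beta-binomial model with an assumed intraclass correlation of 0.3, set a = q(0.7/0.3) and b = (1 - q)(0.7/0.3). The chance of at least one omission among 11 is 1 minus the product of (b + i)/(a + b + i) for i = 0 to 10. At q = 10% (a = 0.233, b = 2.1) this is 37% instead of 69%. At q = 20% (a = 0.467, b = 1.867) it is 62% instead of 91%.

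**6. Dependence on caseload.** At the same q of 10%, a rule that fails an LHW for any omission would flag 69% of those with 11 clients and 34% of those with 4. Equal diligence would look worse in urban sites.

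**The case against.** Several stronger readings are tempting, and the documents do not support them.

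- A reader might infer that the log is checked only against itself. The RA also examines client records, and the protocol (Lady Health Workers) names the two together in the training: "maintaining DMPA client records and re-injection logs". A client in one and missing from the other could be noticed. The gap concerns clients absent from both.
- A reader might infer that an LHW who omits clients will be scored as maintaining the log properly, so that the result is certainly biased upward. No pass criterion is stated and the wording of the questionnaire item is not given. The result could be too high; the documents do not show that it will be.
- A reader might infer that the trial holds a list of first-dose dates. No date field appears in the reproduced screening checklist, and neither document says that a date is recorded. Observation and interview at the same visit only imply one. The count per LHW is the firmer comparator.
- A reader might infer that every first-time entry is a trial client and every trial client belongs in the injecting LHW's log, because the trial aims to "change current policies in Pakistan forbidding initiation of DMPA by LHWs". That policy restricts initiation. It does not define a first-time entry. Eligibility includes women returning after more than six months, whom a log may class as repeat clients. First doses are given at the facility while the LHW is on rotation, and clients may come independently. Nothing says that such a woman must be carried in that LHW's own log.

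It is also fair to say that the outcome is descriptive, that screening is the only powered outcome, and that the protocol's stated interest is whether dates are diligently recorded. All of this limits the weight of the point. What remains is that a listed primary outcome has no scoring rule and no check for missing clients, while a simple comparison is within reach.

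**Conclusion.** The point holds in a limited form. The log outcome rests wholly on papers the LHW keeps and presents herself, so a trial client absent from all of them would not be seen, and the reported proportion could be too high. An independent count of first doses per LHW is available from the trial, averaging about 11 clients per urban LHW and 3 per rural LHW.

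The size of any overstatement cannot be derived. The shares in the working rest on assumed omission rates, on independence or an assumed correlation, and on trial clients being expected in the injecting LHW's log, which the documents do not state. The outcome is LHW-only and descriptive, so neither the non-inferiority test on screening nor the sample size is affected. The change is worth making because it is cheap and the outcome is listed as primary.

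**What to change.** 1. At the interview, set the number of first injections in the LHW's log beside the trial's own record of first doses for that LHW's ID. Add dates and DMPA type where they are captured. No names are needed, in keeping with the protocol's confidentiality section.
2. Report the share of observed first doses found in the log, per LHW and overall. Do not turn it into an all-or-none pass rule, which would penalise higher caseloads.
3. Before the interviews, state in SAP V.C what counts as proper maintenance and how this share enters it. State also whether trial clients are expected in the log of the LHW who gave the first dose, including returning users and women from outside her catchment. If their doses are recorded elsewhere, name the record.
4. Reconcile which LHWs are interviewed (protocol: those above the client threshold; SAP V.B: all), since this sets the denominator.

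Cost: a few minutes per interview and a short list per LHW. The reported proportion may be lower. The check covers trial first doses only, not re-injections or clients outside the trial.
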